9.5 Sample Size

Pre to post treatment assessment using our experimental approach has not been previously conducted, and therefore it is challenging to calculate power to estimate potential sample or effect size comparing the pre to post time-points. The following sample size calculations pertain to the expected changes related the psychophysiological and neurobiological indices to be obtained. The sample size selected for this proposal is based on the detection of between-group significant differences at an alpha of .05 using data collected in our previous study of fear conditioning and extinction recall in controls and patients (PTSD) and using our preliminary fMRI data in women with high (HE) vs. low estradiol (LE) (Zeidan et al, 2011). We have calculated our power to detect between-group differences with a sample size of 25 subjects per group. Based on our previous experience with this population and this paradigm, we expect that (at each of the two time points) it is possible that we will have unusable data in approximately 20% of the subjects due to data of insufficient quality for at least one phase of the experiment. Reasons for this include poor SCR responses, head motion during scanning, or technical difficulties with SCR or fMRI. In addition, we anticipate dropout of ~20 % of patients after the initiation of the study. Thus out of the total of 80 patients, we expect to obtain a full data set (from all time points) from 50 patients. By using the effect size obtained from our previous study (see above), an alpha level of 0.05 and 50 patients, we will have 85% power to detect a significant between-group difference. Regarding the clinical measures, we do not have data to calculate power because of the novelty, but since it is a preliminary proof-of-concept aim, the results to be obtained will help inform future power analyses and calculations for this line of research.

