Population	Sample size is 80 enrolled subjects, 40 at UTHealth Houston, 40 at Penn. Participants will be females ages 18-45 with chronic (at least 1 month post-trauma) DSM-5 FULL PTSD diagnosis and a Clinician-Administered PTSD Scale for DSM-5 (CAPS) Past Month version score ≥ 20 OR chronic (at least 1 month post-trauma) subPTSD diagnosis and CAPS Past Month version score of ≥ 20 (subPTSD defined as: meeting criterion A, F, G, H, and clusters B, C, and at least 1 of the clusters D or E.). Trauma needs to fall under Criterion A. Participants will be on stable medications (for 3 or more months by the time of study entrance), outpatient, and will provide informed consent. For naturally cycling female subjects, stage of menstrual cycle will be ascertained by history, and by serological measures. For women on oral contraceptives, we will identify those using monophasic or biphasic of first, second, third or fourth generation with up to 35mcg of ethinyl estradiol.

Study Sites	UTHealth Houston [REDACTED]
	[REDACTED] University of Pennsylvania Perelman School of Medicine
	[REDACTED]
Number of participants	80 participants expected to be enrolled across 2 sites
Description of Study Agent/Procedure	Study drug will consist of one 2.0 mg dose of estradiol, (obtained from Estrace® Tablets, 2.0 mg estradiol tablets, USP, Warner Chilcott [now Allergan, as Warner Chilcott was acquired by Allergan]) taken orally.
Reference Therapy	Placebo
Key Procedures	Pregnancy Test, Urine Toxicology Screen, fMRI scan, Blood Draw, Estradiol/Placebo Dosage
Statistical Analysis	For all aims, analyses of SCR will test for group x condition interactions for the different groups in each aim with respect to CS+E vs. CS+U. With respect to the fMRI data, the initial analysis will involve assessing for a main effect of group (E vs. Plc), post treatment using CS+E vs. CS+U contrast. In addition, we will compare post treatment brain activations vs. pre-treatment within each group as well as the interactions between time and group also using the same imaging contrast.

Schematic of Study Design

Process Diagram

Visit 0: Telephone Screening

- Local advertising efforts instruct prospective participants to complete a screener
- The Research Assistant/study team member at UTHealth Houston calls and screens individuals for eligibility based off of the screener. Such screening is routine at UTHealth Houston and requires about 30 minutes.

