9.4 Description of Statistical Methods

9.4.1 General Approach

Statistical Methods

SCR Analyses

For all experimental phase, SCR will be computed for each trial by subtracting the mean skin conductance level observed during the last two seconds of context presentation from the maximal skin conductance level reached during CS presentation. All SCR values will be square-root transformed prior to any statistical analyses. To evaluate extinction recall, an extinction retention index (ERI) will be computed for each individual using the following formula: $100 - (\text{mean SCR to the first 4 CS+E trials during recall} / \text{maximum SCR reached during conditioning for this same cue}) * 100$.

Functional MRI analysis

The specific emphasis of the fMRI analysis will be on the extinction recall phase (first four trials of the CS+E vs. first four trials of the CS+U contrast). This contrast has been chosen given the literature demonstrating a significant deficit of PTSD patients during that specific phase of the experimental protocol. BOLD signal will be extracted from the four ROIs (amygdala, dACC, vmPFC and hippocampus). For each of these ROIs, we will use mixed model ANOVAs with time (pre vs. post PE) and group (E2+PE vs. Plc+PE) to investigate main effect of each of these variables as well as group by time interaction. Whole-brain analyses will also be conducted as supplemental analyses for the sake of completeness. We will also conduct regression analyses comparing the change in BOLD responses in each of our ROIs from post- to pre-treatment with PTSD symptom reduction in each of the two groups (E2+PE and Plc+PE).

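### Section 9.5's 50 full data sets from 80 patients match the 20% unusable-data loss counted once; counted at both time points as written, about 41 are expected if losses are independent, and no overlap is stated

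*Combined protocol and SAP*

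**What the plan says.** Section 9.5 (Sample Size) gives two separate losses. On data quality: "at each of the two time points) it is possible that we will have unusable data in approximately 20% of the subjects". The reasons listed are poor SCR responses, head motion and technical difficulties with SCR or fMRI. On attrition: "In addition, we anticipate dropout of ~20 % of patients after the initiation of the study". The conclusion follows directly: "Thus out of the total of 80 patients, we expect to obtain a full data set (from all time points) from 50 patients".

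The power statement uses that number. "We have calculated our power to detect between-group differences with a sample size of 25 subjects per group", and with 50 patients and alpha 0.05 the section claims 85% power for a between-group difference, using an effect size from earlier work that it does not report. The same section says of the pre-to-post comparison that "it is challenging to calculate power to estimate potential sample or effect size comparing the pre to post time-points".

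The planned analyses differ in how many time points they need:

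- **One time point.** The Statistical Analysis row of the Protocol Summary says that for fMRI "the initial analysis will involve assessing for a main effect of group (E vs. Plc), post treatment using CS+E vs. CS+U contrast". For SCR, section 9.4.1 says "an extinction retention index (ERI) will be computed for each individual using the following formula"; the index takes one conditioning session and one recall session from the same experimental visit pair.
- **Both time points.** For each brain region, section 9.4.1 states "we will use mixed model ANOVAs with time (pre vs. post PE) and group (E2+PE vs. Plc+PE") and adds regressions on the change in BOLD response. Hypothesis 1.1 in section 3.1 is a Time x Group interaction.

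**The concern.** The section presents 50 as following from the losses just listed. A patient with a full set from all time points must stay in the study and give usable data at both the first and the second experimental visits. That is three chances of loss at about 20% each, yet 50 is close to what two such losses leave. The section does not say that the same patients are expected to fail twice, or that those with poor baseline data are expected to be the ones who drop out.

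A funder, IRB or DSMB would read the sentence as a forecast of about 50 complete pre-post patients. If about 40 arrive, that could be taken for poor conduct when the stated losses predicted it. The sentence also runs together two counts that serve different analyses: patients with usable post-treatment data, and patients with usable data at both time points.

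**Working it through.** **Inputs, all from section 9.5.** N = 80 (section 5.6 agrees: approximately 80 randomized). Unusable data: 0.20 at each of two time points. Dropout: 0.20, in addition. Stated result: 50 full sets, 25 per group.

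**1. Reproducing the stated 50.** With the unusable-data loss taken once:

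- multiplicative: 80 × 0.8 × 0.8 = 51.2 (25.6 per group)
- additive: 80 × (1 − 0.2 − 0.2) = 48

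Both are within two patients of 50.

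**2. Loss taken at both time points, all losses independent.** 80 × 0.8 × 0.8 × 0.8 = 40.96, about 41 (about 20 per group). The gap from 50 is about 9 patients.

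**3. Allowing overlap.** Expect 80 × 0.2 = 16 dropouts, leaving 64. Expect 80 × 0.2 = 16 patients with unusable baseline data. Among the 64 who stay, expect 64 × 0.2 = 12.8 with unusable post-treatment data. Let s be the share of the 16 baseline failures who are among the dropouts, and r the share of the remaining baseline failures who fail again. Then

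full sets = 64 − 12.8 − 16(1 − s) + 16(1 − s)r = 51.2 − 16(1 − s)(1 − r).

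| s | r | Full sets |
|---|---|---|
| 0 | 0 | 35.2 |
| 0.2 | 0 | 38.4 |
| 0.2 | 0.2 (all independent) | 40.96 |
| 0.2 | 0.5 | 44.8 |
| 0.5 | 0.5 | 47.2 |
| 0.2 | 0.75 | 48.0 |
| 0.75 | 0.2 | 48.0 |
| 0.75 | 0.75 | 50.2 |
| 0.2 | 1 | 51.2 |

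The value s = 0.2 means that dropout is unrelated to baseline data quality. In that case, reaching 50 needs 51.2 − 12.8(1 − r) = 50, so r = 1 − 1.2/12.8 = 0.906: about 91% of baseline failures must recur.

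**4. Approximate inputs.** With 20% dropout and independent failures, 50 full sets need 64(1 − q)² = 50, so q = 1 − √(50/64) = 0.116. That is about 12% unusable per time point, not about 20%. With all three rates at 15%, the count is 80 × 0.85³ = 49.1; at 25%, 80 × 0.75³ = 33.8.

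**5. Post-treatment data alone.** If all dropout comes before the second experimental visits (Visits 10 and 11), 80 × 0.8 × 0.8 = 51.2 patients have usable post-treatment data. If half of the dropouts leave later, 72 attend those visits and 72 × 0.8 = 57.6 have usable data.

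**6. The 85% power.** It cannot be reproduced, because section 9.5 gives no numerical effect size.

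**The case against.** **Overlap is plausible.** Poor SCR response and head motion may persist in the same person, and 50 lies inside the range of 35 to 51. This stands: 41 is conditional on independence, and 50 is not impossible. But technical difficulties need not recur in the same patient, and moderate overlap (half and half) gives 47. Reaching 50 needs strong overlap, which the documents do not state.

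**The inputs are loose.** They are, and 15% for all three losses would give 49. The section nevertheless says about 20%, and its conclusion should follow from that.

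**Dropout timing is not given.** Some patients may leave after Visit 11, during follow-up, and still contribute both scans. Under independent failures, if half of the dropouts do so, 72 × 0.64 = 46 have usable experimental data at both time points; if all do, 80 × 0.64 = 51. So timing matters for the count of usable scans. It does not by itself rescue a full set from all time points, since a dropout breaks that set whenever it occurs. If the sponsor meant the two experimental time points only, section 9.5 should say so.

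**Baseline failures might be replaced.** The documents do not say this. Randomization follows Visit 3 (section 7), usable baseline data is not an eligibility criterion (sections 5.1 and 5.2), and recruitment ends at approximately 80 randomized (section 5.6).

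**The power concerns only a between-group difference.** A post-treatment comparison needs one usable time point, and about 51 is a reasonable count for it under the timing in step 5. Mixed models may also use patients with partial data. But regressions on BOLD change need both time points, and the disputed sentence is itself about full sets.

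**A stronger reading to resist.** A reader might infer that the trial is underpowered. Back-solving an effect size from 85% at 25 per group and applying it to about 20 per group gives about 77%. The documents do not support that figure: they give no effect size and do not say which comparison was powered.

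**Conclusion.** The point holds as a gap between stated inputs and stated result. Fifty corresponds to one unusable-data loss plus dropout. The losses as written give about 41 full sets if independent, about 9 fewer, with a range of about 35 to 51 depending on overlap. The calculation takes the three 20% figures at face value and treats any dropout as breaking a full set. Because the 20% pools SCR and fMRI failures in any phase, the count for a single endpoint may be higher.

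A reader might also infer that 50 is simply wrong, or that more patients are needed. Neither follows. Fifty is attainable with strong overlap, and no loss of power is claimed. What is missing is the assumption that leads to 50, and a clear statement of which analyses it serves. This should be fixed because the only stated power figure rests on that count. Confidence is medium, since the sponsor may have had an overlap in mind that the section does not record.

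**What to change.** Restate the expected counts in section 9.5, for example:

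> With about 20% dropout and about 20% unusable data at each time point, we expect about 41 of 80 patients with a full data set from all time points if losses are independent (about 35 to 51 depending on overlap), and about 51 with usable post-treatment data if dropout occurs before the second experimental visits.

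Alternatively, keep 50 and state and justify the overlap and the dropout timing that it assumes.

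In either case, the sponsor should say which between-group comparison the 85% power at 25 per group refers to. Only the sponsor can supply this, because the section calls pre-to-post power hard to calculate and does not name the comparison used.

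The cost is a few sentences in section 9.5. Sample size, design and analyses stay as they are. The one downside is a less favourable stated count for analyses that need both time points.

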9.6 Measures to Minimize Bias

9.6.1 Enrollment/Randomization/Masking Procedures

The study randomization table is created by the study statistician and provided to the UTHealth Houston and U Penn site pharmacies to be used during the study. A research assistant will be responsible for randomizing the participant by entering the CAPS Severity in REDCap. A randomization number is generated, which is then reported to the Investigational Pharmacy which has the key indicating which randomizations numbers correlate to estradiol or placebo pills. The research team and the subject will be blinded and will not know the investigational product contained in the prescription bottle. The pharmacy has the names of participants in their log. The blind may be broken in the case of an emergency. To request unblinding, after permission to do so is granted by the PI or the study clinical lead, a member of the study team will contact the Investigational Pharmacy to receive the condition of the subject.

10 Source Documents and Access to Source Data/Documents

Source data is all information, original records of clinical findings, observations, or other activities in a clinical trial necessary for the reconstruction and evaluation of the trial. Source data are contained in source documents.

The study case report form (CRF) is the primary data collection instrument for the study. All data requested on the CRF must be recorded. All missing data must be explained. If a space on the CRF is left blank because the procedure was not done or the question was not asked, write "N/D". If the item is not applicable to the individual case, write "N/A". All entries should be printed legibly in blue or black ink or recorded in any direct entry forms. If any entry error has been made, to correct such an error, draw a single straight line through the incorrect entry and enter the correct data above it. All such changes must be initialed and dated. DO NOT ERASE OR WHITE OUT ERRORS. For clarification of illegible or uncertain entries, print the clarification above the item, then initial and date it.

Access to study records will be limited to IRB-approved members of the study team. The investigator will permit study-related monitoring, audits, and inspections by the IRB/EC, the sponsor, government regulatory bodies, and University compliance and quality assurance groups of all study related documents (e.g. source documents, regulatory documents, data collection instruments, study data etc.). The investigator will ensure the capability for inspections of applicable study-related facilities (e.g. pharmacy, diagnostic laboratory, etc.).

Participation as an investigator in this study implies acceptance of potential inspection by government regulatory authorities and applicable University compliance and quality assurance offices.

11 Quality Assurance and Quality Control

QC procedures will be implemented beginning with the data entry system and data QC checks that will be run on the database will be generated. Any missing data or data anomalies will be communicated to the site(s) for clarification/resolution.

Following written SOPs, the study team will verify that the clinical trial is conducted and data are generated, documented (recorded), and reported in compliance with the protocol, GCP, and the applicable regulatory requirements (e.g., Good Laboratory Practices (GLP), Good Manufacturing Practices (GMP)).

The investigational site will provide direct access to all trial related sites, source data/documents, and reports for the purpose of monitoring and auditing by the sponsor, and inspection by local and regulatory authorities.

The investigative team has extensive experience conducting clinical psychotherapy and medication studies for PTSD ([name]) and fMRI methodologies ([name]). They will train and oversee the overall conduct of the staff in clinical trials methodology. They will ensure that on-going supervision is provided, study assessments are completed, and there is good compliance of staff with all research procedures. They will assume responsibility to see that project staff is sufficiently trained to administer project interviews, review assessments with participants, carry out laboratory/scanning procedures, and maintain participants in the study throughout follow-ups. Every quarter, participants' casebooks will be checked by [name] for accuracy with regard to inclusion/exclusion criteria; staff adherence to study procedures; completeness; and documentation of participant attrition, adverse events, and sources of potential protocol violations. Discrepancies will be noted, brought to the attention of the PI and project staff, investigated and resolved. IEs and RAs will be given specific training on follow-up methods similar to those of our numerous prior studies, and a set of MINI and CAPS recordings will be reviewed to assess inter-rater reliability for each independent evaluator prior to the start of independent evaluations. The criterion of each tape in the set will be 80% agreement, with agreement on the CAPS defined as the scores of the rater within 10% of the total scale range.

Before beginning any experimental procedures, [name] provide extensive training to all team members regarding data acquisition and maintenance as well as safety of participants. [name] will also run data quality checks every 3 months to ensure adequate quality and consistency of fMRI and SCR data.

12 Ethics/Protection of Human Subjects

12.1 Ethical Standard

This study is to be conducted according to US and international standards of Good Clinical Practice (FDA Title 21 part 312 and International Conference on Harmonization guidelines), applicable government regulations and Institutional research policies and procedures.

This protocol and any amendments will be submitted to The UTHealth Houston Institutional Review Board (IRB), in agreement with local legal prescriptions, for formal approval of the study conduct. The decision of the IRB concerning the conduct of the study will be made in writing to the investigator and a copy of this decision will be provided to NIH before commencement of this study.

All subjects for this study will be provided a consent form describing this study and providing sufficient information for subjects to make an informed decision about their participation in this study. See Attachment A for a copy of the Subject Informed Consent Forms. These consent forms will be submitted with the protocol for review and approval by the IRB for the study. The formal consent of a subject, using the IRB-approved consent form, must be obtained before that subject undergoes any study procedure. The consent form must be signed by the subject or legally acceptable surrogate, and the investigator-designated research professional obtaining the consent.

12.2 Institutional Review Board

The protocol, informed consent form(s), recruitment materials, and all participant materials will be submitted to the IRB for review and approval. Approval of both the protocol and the consent form must be obtained before any participant is enrolled. Any amendment to the protocol will require review and approval by the IRB before the changes are implemented to the study. All changes to the consent form will be IRB approved; a determination will be made regarding whether previously consented participants need to be re-consented.

12.3 Informed Consent Process

Consent forms describing in detail the study intervention, study procedures, and risks are given to the participant and written documentation of informed consent is required prior to starting intervention. The following consent materials are submitted with this protocol:

1. Consent for adult participants
2. Video consent for adult participants
3. Audio consent for adult participants
4. Consent for adult participants for training study
5. Video consent for adult participants for training study

12.3.1 Consent Procedures and Documentation

Informed consent is a process that is initiated prior to the individual's agreeing to participate in the study and continues throughout the individual's study participation. Extensive discussion of risks and possible benefits of participation will be provided to the participants (and their families, if requested). Consent forms will be IRB-approved and the participant will be asked to read and review the document. The investigator will explain the research study to the participant and answer any questions that may arise. All participants will receive a verbal explanation in terms suited to their comprehension of the purposes, procedures, and potential risks of the study and of their rights as research participants. Participants will have the opportunity to carefully review the written consent form and ask questions prior to signing. The participants should have the opportunity to discuss the study with their surrogates or think about it prior to agreeing to participate.

Written or electronic (via REDCap) informed consent will be obtained by one of the IRB approved UTHealth Houston study investigators prior to participation in the study. Subjects must be competent to provide informed consent. Study procedures and potential risks and benefits will be described to subjects at the time participation in the study is sought. Ample opportunity will be provided for potential subjects to carefully read the consent form and to ask any questions they may have. The PI will retain copies of the signed consent

form patients will be given a copy of the consent form. A subject may end their study participation at any time if they chose to do so.

A copy of the signed informed consent document will be stored in the subject's research record. The consent process, including the name of the individual obtaining consent, will be thoroughly documented in the subject's research record. Any alteration to the standard consent process (e.g. use of a translator, consent from a legally authorized representative, consent document presented orally, etc.) and the justification for such alteration will likewise be documented.

